13.3 Methods for Resistance Testing

13.3.1 Isolation & Identification of Organisms Using Microbiological Techniques

Various organisms from nasal, nasopharyngeal, and rectal swabs will be isolated using the media and conditions in Table 2 and identified using the methods summarized in Table 3 and below. Standard microbiological handbooks should be referenced for more detailed information.

Procedure for Masking Samples

The microbiologist and all lab staff will be masked to the community of origin.

Laboratory Results Reporting

All lab results will be kept in computer files as well as in hard-copy form by the Microbiologist.

Table 2. Isolation of Organisms from Source - Primary Plating Media & Incubating Conditions

Source	Media	Incubation	Organisms Isolated
Nasal Swab	Blood and MSA	35°C	S. aureus (core)
		5% CO ₂	
Nasopharyngeal	Blood and Strep	35°C	S. pneumoniae (core)
Swab	select plate,	5% CO ₂	H. influenzae (non-core)
	chocolate, chocolate		N. meningitidis (non-core)
	with bacitracin		
Rectal Swab	Blood and	35°C	E. coli (core)
	MacConkey		

Table 3. Identification of Organisms

Organism	Stain	Identification Tests
S. aureus	Gram stain	Catalase and Tube Coagulase or latex
(core)		agglutination reagent
S. pneumoniae	Gram stain	Catalase, Optochin disc and/or Desoxycholate
(core)		reagent, alpha-hemolytic on blood agar
H. influenzae	Gram stain	Satelliting growth on blood agar, ALA or other
(non-core)		identification tests
N. meningitidis	Gram stain	Sugars utilization or other identification kit
(non-core)		
S. pyogenes	Gram stain	Catalase, beta-hemolytic on blood agar, and
(core)		Bacitracin disc or PYR test
E. coli	Gram stain	Indole, oxidase, beta-hemolytic on blood agar,
(core)		PYR and other identification tests as required

Description of Identification Tests:

We will follow the standard quality control methods already in place at the laboratory. For example, lab staff will perform positive and negative growth controls for all media, and positive controls for all stains and identification tests at a pre-determined schedule.

Catalase Test:

A few drops of 3% hydrogen peroxide are added to colonies removed from agar and smeared onto a clean glass slide, and immediately observed for the release of oxygen or "bubbling." Bubbling is interpreted as the presence of catalase. Lack of bubbling is a negative test.

Tube Coagulase:

Coagulase plasma is inoculated with an isolated staphylococcal colony and incubated for up to 24 hours at 37°C. Any degree of clot formation is a positive reaction and no clot is a negative reaction.

Latex Agglutination:

A few staphylococcal colonies are mixed with the latex agglutination reagent and observed for agglutination. A positive reaction is agglutination of the latex particles, while no agglutination is a negative reaction.

Optochin Test:

An optochin disc is placed onto a blood agar subcultured plate that has been inoculated with a pure culture of the test organism. Plates are incubated for 24

hours at 35°C in CO₂. If a zone of inhibition of 14 mm or more is formed, then it's *S. pneumoniae*.

Desoxycholate (10%) *Test*:

A drop of reagent is added to a well-isolated colony on a blood agar plate. Colonies of *S. pneumoniae* will disintegrate after 30 minutes.

Satelliting Growth on Blood Agar:

Colonies resembling Haemophilus are subcultured to a non-selective blood agar plate and cross streaked with Coagulase negative Staphylococcus. Plates are incubated in CO₂ overnight and examined for satellite growth around Staphylococcus.

ALA Test:

Sugars Utilization Tests:

Indole Test:

Oxidase Test:

PYR Test:

13.3.2 Microbiological Resistance Testing for Swabs

Resistance testing will be performed using the Kirby Bauer disc diffusion assay or E-test strips (to determine MIC's).

Quality Control

E. coli ATCC 25922, S. pneumoniae ATCC 49619, H. influenzae ATCC 49247, S. aureus ATCC 25923 and 29213 are used for quality control testing of antibiotic discs and E-test strips.

Kirby Bauer Assay

A suspension of the isolate is prepared and turbidity adjusted until it reaches the 0.5 McFarland standard. The suspension is used to inoculate the appropriate susceptibility agar plate for confluent growth. The plate is allowed to dry. Antimicrobial disks are placed on the agar plates with sterile forceps or tweezers; disks may not be moved once they have touched the plates. After the disks are placed on the plate, the plates are inverted and incubated at 35°C for 16 to 18 hours. After incubation, the diameter of the zones of complete inhibition (including the diameter of the disk) (Figure 2) are measured and recorded in millimeters. The measurements can be made with a ruler or sliding caliper on the

undersurface of the plate without opening the lid. The zones of growth inhibition will be compared with the zone-size interpretative table and recorded as susceptible, intermediate, or resistant to each drug tested according to CLSI guidelines (see Appendix).

Figure 2. Results of the disk diffusion assay. This *Shigella* isolate is resistant to trimethoprim-sulfamethoxazole and is growing up to the disk (SXT), the zone of which is recorded as 6 mm.

E-test strips.

In addition, azithromycin Minimum Inhibitory Concentrations (MIC) are determined using E-test strips. A suspension of the isolate is prepared and turbidity adjusted until it reaches the 0.5 McFarland standard. The suspension is used to inoculate the appropriate susceptibility agar plate for confluent growth. The plate is allowed to dry. E-test strips are placed on the agar plates with sterile forceps or tweezers; strips may not be moved once they have touched the plates. After the strips are placed on the plate, the plates are inverted and incubated at 35°C for 20 to 24 hours. The MIC is read where the ellipse intersects the MIC scale on the strip. The MIC will be compared with the interpretative table according to CLSI guidelines (see Appendix).

Table 4. Antibiotics Testing Guidelines

Specimen	Organism	Antibiotics Tested
Nasal	S. aureus	Azithromycin, cefoxitin
Nasopharyngeal	S. pneumoniae	Azithromycin, clindamycin, penicillin
	H. influenzae	(Note: S. pneumoniae - 1 ug oxacillin used to
	N. meningitidis	predict penicillin resistance for Kirby Bauer)
Stool	E. coli	Azithromycin, ampicillin, co-trimoxazole

Materials Required for Susceptibility Testing:

- MH w/ 5% sheep blood plates
- MHA plates
- MH broth or sterile 0.85% saline
- Sterile cotton-tipped swabs
- 0.5 MacFarland Standard
- Blood and chocolate plates
- Caliper for reading zones
- Forceps
- Light source
- Vortex
- 35°C ambient air and 35°C CO₂ incubator

13.3.3 Nucleic Acid Based Resistance Testing for Stool Specimens

Stool specimens not cultured will undergo nucleic acid based resistance testing. DNA from the stool samples will be extracted using some type of DNA isolation kit (i.e. Norgen Stool DNA Isolation Kit) and the appropriate corresponding protocol.⁴⁹ PCR and gel electrophoresis will then be performed with specific primers to detect genes associated with *E. coli* and antibiotic resistance (specifically macrolide resistance).

Extracting DNA from Stool Procedure

1. Lysate Preparation

- a. Mix the sample well to make sure that the stool/preservative mixture is homogenous. Carefully remove the lid from the collection tube and aliquot 200 μ l of the stool/preservative liquid and add it to a Bead Tube provided with the kit (it may be easier to use a pipet tip that has been cut to make the opening wider or to use a large orifice pipet tip).
- b. Add **Lysis Solution** to the Bead Tube, so that the final volume is 1 ml (for our purposes, add 800 μ l of Lysis Solution). Vortex and centrifuge briefly.
- c. Add 100 µl of **Lysis Additive** and vortex briefly.
- d. Secure the Bead Tube horizontally on a flat-bed vortex pad with tape, or secure the tube in any commercially available bead beater equipment (e.g. Scientific Industries' Disruptor GenieTM). Vortex for 3 minute at maximum speed.
- e. Centrifuge the tube for 2 minutes at $14000 \times g$ (~14,000 RPM).
- f. Transfer up to 600 µl of supernatant to a DNAase-free microcentrifuge tube (not provided).
- g. Add 200 μ l of **Binding Solution**, mix by inverting the tube a few times, and incubate for 10 minutes on ice.
- h. Spin the lysate for 2 minutes to pellet any cell debris.
- i. Using a pipet, transfer up to 700 μ l of supernatant (avoid contacting the pellet with the pipet tip) into a 2 ml DNAase-free microcentrifuge tube (not provided).
- j. Add an equal volume of 70% ethanol (provided by the user) to the lysate collected above (100 μ l of ethanol is added to every 100 μ l of lysate). Vortex to mix.

2. Binding to Column

- a. Assemble a spin column with one of the provided collection tubes.
- b. Apply 600 μ L of the clarified lysate with ethanol onto the column and centrifuge for 1 minute at 14000 \times g (~14,000 RPM). Discard the flow through and reassemble the spin column with the collection tube. **Note:** Ensure the entire lysate volume has passed through into the collection tube by inspecting the column. If the entire lysate volume has not passed, spin for an additional minute.
- c. Repeat step 2b with the remaining volume of lysate mixture.

3. Column Wash

- a. Apply 500 μ L of **Wash Solution I** to the column and centrifuge for 1 minute.
 - **Note:** Ensure the entire wash solution has passed through into the collection tube by inspecting the column. If the entire wash volume has not passed, spin for an additional minute.
- b. Discard the flow through and reassemble the spin column with its collection tube.
- c. Apply 500 µL of **Wash Solution II** to the column and centrifuge for 1 minute.
- d. Discard the flow through and reassemble the spin column with its collection tube.
- e. Repeat 3c and 3d.
- f. Spin the column for 2 minutes in order to thoroughly dry the resin. Discard the collection tube.

4. DNA Elution

- a. Place the column into a fresh 1.7 mL Elution tube provided with the kit.
- b. Add 50 μL of Elution Buffer to the column.
- c. Centrifuge for 2 minutes at 200 x g (\sim 2,000 RPM), followed by a 1 minute spin at 14,000 x g (\sim 14,000 RPM). Note the volume eluted from the column. If the entire volume has not been eluted, spin the column at 14,000 x g (\sim 14,000 RPM) for 1 additional minute.
- d. (Optional): An additional elution may be performed if desired by repeating steps 4b and 4c using 50 μ L of Elution Buffer. The total yield can be improved by an additional 20-30% when this second elution is performed.

5. Storage of DNA

The purified genomic DNA can be stored at 2-8°C for a few days. For longer term storage, -20°C is recommended.

Amplifying Gene Regions

We will use DNA extracted from stool specimens and published primers to perform PCR reactions for the genes of interest:50-52

Purpose	Genes
Detecting E. coli	malK (encodes for malB promoter) 53
	*This gene will detect for both E. coli and Shigella since the two are closely related and are difficult to discriminate from one another.
Detecting Antibiotic	mph (A, B)
Resistance	erm (A, B, C)
	mef (A)
	ere (A, B)
	msr(A)

13.4 Methods for Chlamydia trachomatis

13.4.1 Description of Abbott RealTime Assay

Swabs will be processed with the Abbott RealTime assay for *C. trachomatis*, using the automated Abbott *m*2000 System. The RealTime assay targets the cryptic plasmid of *C. trachomatis*. The assay has been shown to be highly sensitive and specific for the diagnosis of sexually transmitted *C. trachomatis*, with sensitivities exceeding that of the nucleic acid amplification test used in most recent trachoma studies (Roche AMPLICOR).^{54,55}

13.4.2 Processing of Samples for PCR

Samples are handled as per Abbott RealTime sample processing protocol, with the following modifications:

- 1. Samples are boiled for 10 minutes at 100°C. Boiling of samples is an accepted treatment method to remove substances that may be inhibitory to the PCR amplification process
- 2. Samples are pooled.

13.4.3 Procedure for Masking Samples

In order to mask the location origin, the control status, and the clinical exam grading of the conjunctival samples collected in the field, the Database Manager will assign an identification number different from the random number assigned to each child. The PCR results will be recorded according to this laboratory

identification number, thus masking the lab until all the samples have been processed. The Database Manager will then link the lab ID number to the random sample number to reveal the test results by village.

13.4.4 Procedure for Pooling Samples

We will increase the efficiency of chlamydial testing by combining swabs from the same age stratum and same community into pools of 5 random swabs for processing. An internal control will be run with each pool to rule out the possibility of PCR inhibitors. Any inhibitory pools will be re-tested, and if still inhibitory, the swabs will be individually re-tested. If PCR from any pool is equivocal, then all swabs from the pool will be tested individually. While samples will necessarily be diluted in this process, this is not thought to affect the sensitivity of the test. 56 We will unpool all positive pools in the 0-5 year age stratum and estimate the community prevalence of chlamydial infection as the proportion of positive swabs. We will estimate the community prevalence of infection in the 6-9 and \geq 10 year age strata using maximum likelihood estimation, similar to our previous trials: the number of individual swabs with the maximum likelihood of having resulted in the observed pooled results will be chosen as the estimate for that village. 57,58

In order to pool the conjunctival samples in the lab, the microbiology lab staff will assign a new pool ID number for every sample, and samples will be stored at -80°C freezer until PCR testing (if not processed that day).

13.4.5 Quality Control

- 1. A *C. trachomatis*(+) control and a *C. trachomatis*(-) control (targeting 136 base pairs of a pumpkin gene) is included in each test run of the Abbott RealTime assay.
- 2. To test the effect of sample processing, a known positive sample is processed and tested in each test run. (This control is helpful when testing large numbers of negative samples.)
- 3. An internal control intended to identify specimens that contain polymerase inhibitor is run routinely on each sample. The internal control helps identify false negative results.

13.4.6 Quantification

For every 0-5 year old who tests positive for chlamydia, we will also run PCR for the beta actin gene on the same sample, in order to normalize the quantity of chlamydial DNA to the amount of the specimen. Quantitative results from the Abbott system are given in terms of a decision cycle (DC) number. We will generate a ratio of the DC number of the chlamydial DNA to the DC number of the beta actin gene and use the resulting ratio as the chlamydial load.

Chapter 14: Study Medication

Children aged 1-60 months on the current census will be offered weight- or height-based, directly observed, oral suspension (azithromycin or placebo) every 6 months for 2 years (as performed in trachoma programs) at each study site. In addition to being at least 1 month of age, children should weigh at least 3.8 kg to be eligible for treatment. This ensures that mistakenly aged or premature infants won't be treated. These infants will be eligible for treatment at the subsequent distribution, approximately 6 months later. The mortality application will not provide a dose for children weighing <3.8 kg.

We will monitor adverse events following mass treatments as described in the adverse events section. The treatment and monitoring schedule for all study arms is shown in Table 1.

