5.2.2. Non-core Elements

The designation "non-core" element means that study sites may choose if they wish to perform the study activity. If the study sites perform the study activity, the methodology will be performed according to this protocol so that the 3 sites may be more easily compared. Sites may choose to perform several non-core morbidity assessments at the 0, 12, and 24 month visits:

- Nasal swabs for macrolide resistance in *Staphylococcus aureus*
- Conjunctival swabs for Chlamydia trachomatis
- Conjunctival examination and photography to assess for trachoma
- Anthropometric assessments
- Nasopharyngeal swab collection at local health posts to compare macrolide resistance in the community with that in the health post

In addition, there are several non-core activities that occur outside the annual morbidity/resistance assessment:

- Additional study visit during the first malaria season to collect blood samples for malaria and anemia testing
- Clinic-based case finding for childhood illnesses at all health clinics in the study area

Costs

We anticipate recording the cost of distributions in a random subset of 12 villages at the 6 or 12 and 24 month visits.

Details of the non-core elements for each study site can be found in the Appendices.

Chapter 6: Census

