2.1.2 Morbidity Trials

Primary Analyses (Morbidity Study).

The morbidity analyses are to be conducted on a country-specific basis. Each outcome will be addressed in a separate analysis. Outcomes are taken at 0, 12, and 24 months.

The outcome and analysis plan for all non-core studies must be submitted to the Steering Committee for approval.

The outcomes for this study are listed on www.clinicaltrials.gov. Analyses may be conducted at the village level (accounting thus for clustering), or, when possible, at the individual level accounting for clustering by using mixed effects regression. The listed primary outcomes (4 February 2015) are:

- 1. Height over time in children aged 1-60 months (Niger & Malawi)
- 2. Weight, corrected for height over time in children aged 1-60 months (Niger & Malawi)
- 3. Fraction of macrolide resistance in nasopharyngeal swabs in children 1-60 months (core). Note that for Niger, this is phenotypic, and is a binary outcome at the individual level.
- 4. Fraction of macrolide resistance from stool specimens in children 1-60 months (core). For Niger, this includes RNA, DNA, and TAC-card methods (a binary outcome at the individual level).
- 5. Fraction of macrolide resistance by nasal swabs in children 1-60 months (Niger only). For Niger, this is based on RNA and DNA sequencing (a binary outcome at the individual level).
- 6. Presence of malaria parasites in children 1-60 months (core activity)
- 7. Fraction of conjunctival swabs yielding ocular chlamydia in children 1-60 months (Niger)

Nonnormality, heteroskedasticity, clustering, and outliers will be assessed appropriately.

Secondary Analyses (Morbiditiy Study).

Common templates will be used. Analysis will use cluster-level variables for malaria parasites, macrolide resistance in NP swabs, macrolide resistance in nasal swabs, macrolide resistance in stool specimens, and ocular chlamydia. Clustered logistic regression using baseline values will be used, with the outcome being the 12 and 24 month observations, and time and treatment as covariates in addition to baseline values. Permutation P-values will be reported.

Model checking will be performed to identify poorly fitting models, using the residuals versus fitted values plot and by finding high leverage points. Significance testing will be conducted using permutation tests.

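### Chlamydial load in Protocol 13.4.6 is a ratio of two PCR cycle numbers, which only partly removes the amount of specimen and, on the usual meaning of a cycle number, falls as chlamydial DNA rises

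*Protocol*

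**What the plan says.** Protocol 13.4.6 covers a subset of swabs: "For every 0-5 year old who tests positive for chlamydia, we will also run PCR for the beta actin gene on the same sample". It gives the purpose of the second assay as "in order to normalize the quantity of chlamydial DNA to the amount of the specimen". On the scale of the output it says: "Quantitative results from the Abbott system are given in terms of a decision cycle (DC) number". The measure is then defined: "We will generate a ratio of the DC number of the chlamydial DNA to the DC number of the beta actin gene". The protocol will "use the resulting ratio as the chlamydial load".

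The section gives no antilog, subtraction, standard curve or reversal of sign, and does not say whether a decision cycle (DC) number rises or falls with the amount of target. No other section supplies any of these.

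Two other places fix the status of the measure. Protocol 5.2.2 lists "Conjunctival swabs for Chlamydia trachomatis" among the non-core assessments, and says that a site choosing such an activity follows the protocol's method. SAP 2.1.2 lists the chlamydia outcome as a prevalence ("Fraction of conjunctival swabs yielding ocular chlamydia in children 1-60 months (Niger"), not as a load.

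**The concern.** The section states an aim and then gives a formula that does not meet it. To normalise one DNA quantity to another is to divide the quantities. A cycle number is a logarithm of quantity, so division of quantities becomes subtraction of cycle numbers. Dividing the cycle numbers themselves leaves part of the specimen amount in the result.

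There is a second, weaker fault. A PCR cycle number ordinarily means the number of cycles needed for detection, so more starting DNA gives a smaller number. With the chlamydial number in the numerator, what is called load would then go down as chlamydial DNA goes up.

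At stake is any load result that a site reports. Differences in how much material the swab picked up would enter a measure meant to remove them, the values could not be read as fold differences in DNA, and a reader could take the direction the wrong way round.

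**Working it through.** The documents give no DC values, no amplification efficiency and no load figure, so there is no planned number to reproduce. The DC pairs and dilutions below are illustrations.

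**Inputs**
- Definition: ratio = DC(chlamydia) / DC(actin), from Protocol 13.4.6.
- Assumed: DC = K - log(copies), with the logarithm to base 1 + E. The efficiency E is 1.0 (doubling per cycle) unless stated; the range tried is 0.9 to 1.0.
- Multiplying the specimen by s multiplies both targets by s, so both DCs fall by log2(s) when E = 1. For a ten-fold change, log2(10) = 3.32 cycles.
- Apparent fold change in load = 2^(DC(chlamydia) - DC(actin) × new ratio). This is the change in chlamydial DNA at unchanged actin that would give the same new ratio.

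**Specimen amount, with chlamydial DNA per unit of actin unchanged**

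Start at 30/25 = 1.200.
- Ten-fold less specimen: 33.32/28.32 = 1.177. Apparent load change 2^(30 - 25 × 1.1765) = 1.5-fold.
- Hundred-fold less: 36.64/31.64 = 1.158. Apparent change 2.1-fold.
- The DC difference is 5 cycles in all three cases.

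Other assumed pairs, with ten times more specimen:

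| DC chlamydia / actin | Ratio before | Ratio after | Apparent load (true = 1) | Size of distortion |
|---|---|---|---|---|
| 30/22 | 1.364 | 26.68/18.68 = 1.428 | 0.37 | 2.7-fold |
| 36/22 | 1.636 | 32.68/18.68 = 1.750 | 0.18 | 5.6-fold |
| 30/18 | 1.667 | 26.68/14.68 = 1.818 | 0.15 | 6.6-fold |
| 22/26 | 0.846 | 18.68/22.68 = 0.824 | 1.50 | 1.5-fold |
| 25/25 | 1.000 | 21.68/21.68 = 1.000 | 1.00 | none |

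At E = 0.9 the 30/18 row becomes 6.8-fold. The distortion vanishes only when the two DCs are equal, and its direction depends on which DC is larger.

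**Ranking.** Child B has 30/22, ratio 1.364. Child A has twice the chlamydial DNA per unit of actin and ten times the specimen: (30 - 1 - 3.32)/(22 - 3.32) = 25.68/18.68 = 1.375. Even if a smaller ratio is read as more load, A ranks below B. The DC differences, 7 for A and 8 for B, rank them correctly.

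**Direction, with specimen fixed.** From 30/25 = 1.200, ten-fold more chlamydial DNA gives 26.68/25 = 1.067 and hundred-fold more gives 23.36/25 = 0.934. The ratio fell in every pair tried, at both efficiencies.

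**If DC instead rose with target.** Score it as 40 minus the cycle count (40 is an assumed cut-off). The 30/22 example becomes 10/18 = 0.556. With ten-fold less specimen it is 6.68/14.68 = 0.455, and with ten-fold more 13.32/21.32 = 0.625. The direction fault goes, but the dependence on specimen amount stays.

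**The case against.** The best case against raising this is that no planned analysis uses load. SAP 2.1.2 lists the fraction of swabs positive, and its secondary template applies clustered logistic regression to ocular chlamydia. Protocol 13.4.4 estimates prevalence from swab results. The conjunctival sequencing analyses in SAP 2.1.3 use reads or OTUs. The Niger contingency study takes no conjunctival swabs. All of this stands, and it limits the consequence.

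Three stronger readings are tempting, and the documents do not support them.
- A reader might infer that the ratio does no normalising at all. It does some: in the 30/25 example, ten-fold less specimen leaves a 1.5-fold shift where an uncorrected DC would show ten-fold. The fault is incomplete normalisation.
- A reader might infer that the trial would report the arms the wrong way round. The plan contains no comparison of load between arms, so that is hypothetical. With actin fixed the ratio is also monotone, so the direction could be recovered by relabelling.
- A reader might treat the inverse direction as documented. It rests on the ordinary meaning of a cycle number, and 13.4.6 is silent on it.

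The repair has limits too. Reading 2^(difference) as a fold change assumes that both targets amplify with equal and near-complete efficiency, and the documents give no efficiencies. The assay targets the cryptic plasmid (Protocol 13.4.1), so the result is relative plasmid DNA, not necessarily organisms.

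None of this makes the ratio achieve the purpose stated for it.

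**Conclusion.** The point holds in a limited form. The formula in 13.4.6 does not deliver the normalisation that the section gives as its reason. That follows from the log scale of cycle numbers and does not depend on which way DC runs. Under the assumed DC pairs, a ten-fold change in specimen leaves an apparent load change from none (equal DCs) to about 6.6-fold at doubling per cycle, or 6.8-fold at efficiency 0.9. The sizes are illustrative because the documents give no DC values.

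The label is also wrong if a lower cycle number means more DNA, which is the usual meaning but is not stated.

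The effect is confined to a non-core measure in chlamydia-positive 0-5 year olds that is not a listed SAP outcome. Any load result reported would be distorted and could be misread in direction. The change is worth making because it costs so little and because sites that take up the activity are bound to this method.

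**What to change.** In Protocol 13.4.6, replace the ratio with normalised log load = DC(beta actin) - DC(chlamydia). State the direction of the DC scale, and that a higher value means more chlamydial (plasmid) DNA per unit of specimen. Analyse the measure on the log scale. Report fold differences as 2^(difference) only under a stated assumption of equal and near-100% amplification efficiency for the two targets; otherwise use the assay efficiencies.

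The cost is a short rewording and one line of code. The difference uses the same two readings and needs no new laboratory work, and any ratios already computed can be recalculated from stored DC values. Converting both readings to quantities with a standard curve would also work, but might need calibration runs that the protocol does not describe.
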